8.6.3.1 Clinical Dementia Rating Scale

Clinical Dementia Rating Scale is a global assessment instrument that yields global score and a sum of boxes score. The Clinical Dementia Rating Scale is derived from a semi-structured interview with the participant and an appropriate informant, and it rates impairment in 6 categories (memory, orientation, judgment and problem solving, community affairs, home and hobbies, and personal care) on a 5-point scale for which 0 = no impairment, 0.5 = questionable impairment, and 1, 2, and 3 = mild, moderate, and severe impairment, respectively. From the 6 individual category ratings, or box scores, the Clinical Dementia Rating Scale – Global Score is established by clinical scoring rules, for which the Clinical Dementia Rating of 0 = no dementia and Clinical Dementia Rating of 0.5, 1, 2, or 3 = questionable, mild, moderate, or severe dementia, respectively (Morris, 1993). The Clinical Dementia Rating Scale – Sum of boxes score is a detailed quantitative general index that provides more information than the Clinical Dementia Rating Scale – Global Score in participants with early (prodromal to mild)

Protocol TB006AD2102

Protocol Date and Version: 15 Oct 2021; v 3.0

dementia (Coley et al, 2011; Cedarbaum et al, 2013). In particular, the Clinical Dementia Rating Scale – Sum of Boxes has been proposed for use in longitudinal assessment of dementia and is widely used in AD studies as a global measure of disease progression (Williams et al, 2013).

8.6.3.2 Mini-mental State Examination

The MMSE is a brief 30-point questionnaire used to assess cognitive impairment with lower scores indicating greater impairment. The MMSE assesses 11 categories of cognition including orientation to time, memory, attention, concentration, naming, repetition, comprehension, and the ability to create a sentence and to copy 2 intersecting polygons. The total scores on the scale ranges from 0 to 30 with lower scores indicating greater impairment.

The MMSE will be administered at the time points indicated in the SoA (Table 1 and Table 2). The MMSE will be administered by a trained member of the investigational team. At each site, the same individual, whenever possible, will perform the MMSE evaluation on a specific patient throughout the study. The screening MMSE will be used for purposes of determining patient eligibility and does not need to be reconciled with the baseline MMSE score.

8.6.3.3 Cognitive Drug Research System

The Cognitive Drug Research system is an automated battery amenable to measurement of cognitive deficits in patients with AD. It consists of performance tasks measuring attention, working memory, episodic memory and executive function. It contains 11 tests and is performed on a tablet-like device. The average duration of the battery is approximately 25 minutes.

The Cognitive Drug Research system is performed at the time points listed in the SoA (Table 1 and Table 2). Two training sessions will be conducted at least 30 minutes apart during the screening period to allow patients to become familiar with the procedure, reduce test anxiety, reduce learning effects, and produce a stable baseline assessment.

8.6.3.4 Neuropsychiatric Inventory

The NPI is a rater-administered, fully structured interview in which all questions are provided and read verbatim. The sole source of information is the interview with a caregiver who knows the patient well. This study uses the NPI version with 10 behavioral domains: delusions, hallucinations, agitation/aggression, depression/dysphoria, anxiety, elation/euphoria, apathy/indifference, disinhibition, irritability/lability, and aberrant motor behavior.

[figure not shown]
The NPI total score is calculated by adding the scores of the domains (each domain scores ranges from 0 to 12). The NPI total score ranges from 0 to 120 with higher scores indicating greater behavioral impairment.

The NPI-D scores in each of the domains are not included in the NPI total score. The NPI-D total score is calculated by adding the scores of caregiver distress in each of the domains (score ranges from 0 to 5 in each domain). The NPI-D total score ranges from 0 to 50 with higher scores indicating greater distress.

Protocol TB006AD2102

Protocol Date and Version: 15 Oct 2021; v 3.0

The NPI will be administered at the time points indicated in the SoA (Table 1 and Table 2). The NPI will be administered by an independent, trained, and certified member of the investigational team. At each site, the same individual, whenever possible, will perform the NPI evaluation on a specific patient throughout the study.

8.7 Pharmacogenetics

A 2 ml sample of blood will be taken for ApoE4 genotyping at screening from patients who give separate written informed consent for this optional research. If this sample is not taken at screening, it may be taken at any visit until the last study visit.

A general analysis of deoxyribonucleic acid will not be employed. However, other targeted analyses of genetic polymorphisms in AD may be conducted.

Instructions for collection, processing, labelling, storing and shipping samples are detailed in the Laboratory Manual.

Protocol TB006AD2102

Protocol Date and Version: 15 Oct 2021; v 3.0

8.8 Immunogenicity Assessments

Antibodies to TB006 will be evaluated in plasma samples collected from all patients at the time points according to the SoA (Table 1 and Table 2). These samples will be tested by the sponsor or sponsor's designee.

Anti-TB006 antibodies will be determined on plasma samples collected for plasma PK determinations, and no additional blood samples need to be obtained.

Plasma samples will be screened for antibodies binding to TB006 and the titer of confirmed positive samples will be reported. Other analyses may be performed to verify the stability of antibodies to TB006 and/or further characterize the immunogenicity of TB006.

The detection and characterization of antibodies to TB006 will be performed using a validated assay method by or under the supervision of the sponsor. All samples collected for detection of antibodies to study drug will also be evaluated for TB006 plasma concentration to enable interpretation of the antibody data. Antibodies may be further characterized and/or evaluated for their ability to neutralize the activity of the study drug(s).

8.9 Total Volume of Blood Sampling

Table 6 and Table 7 presents the number of blood samples and the total volume of blood that will be collected throughout the study (Parts 1 and 2).

Table 6. Summary of Blood Sample Volumes for Part 1

	Approximate Sample Volume per Collection (mL)	Number of Collection Time Points	Approximate Total Volume Collected (mL)
Clinical laboratory tests ^a	12.5	6	$12.5 \times 6 = 75$
Viral serology	3.5	1	$3.5 \times 1 = 3.5$
PK and/or ADA blood sampling	5	22	$5 \times 22 = 110$
Pharmacogenetic sampling (optional)	2	1	2
PD blood sampling	6	3	6×3 = 18
Total Blood Volume Estimate			208.50

ADA = anti-drug antibody; PD = pharmacodynamic(s); PK = pharmacokinetic(s).

a 12.5 mL sample for hematology, clinical chemistry, and includes serum pregnancy test where this is performed at the same time point.

Protocol TB006AD2102

Protocol Date and Version: 15 Oct 2021; v 3.0

Table 7. Summary of Blood Sample Volumes for Part 2

	Approximate Sample Volume per Collection (mL)	Number of Collection Time Points	Approximate Total Volume Collected (mL)
Clinical laboratory tests ^a	12.5	6	$12.5 \times 6 = 75$
Viral serology	3.5	1	$3.5 \times 1 = 3.5$
PK and/or ADA blood sampling	5	8	$5 \times 8 = 40$
Pharmacogenetic sampling (optional)	2	1	2
PD blood sampling	6	3	$6 \times 3 = 18$
Total Blood Volume Estimate			138.50

ADA = anti-drug antibody; PD = pharmacodynamic(s); PK = pharmacokinetic(s).

a 12.5 mL sample for hematology, clinical chemistry, and includes serum pregnancy test where this is performed at the same time point.

Protocol TB006AD2102

Protocol Date and Version: 15 Oct 2021; v 3.0

9 STATISTICAL CONSIDERATIONS

9.1 Statistical Hypotheses

The primary endpoint in Part 2 is the change from baseline Clinical Dementia Rating Scale – Sum of Boxes score at through Day 104. The primary null hypothesis to be tested is as follow:

• H₀: There is no difference between TB006 group and placebo group in change from baseline Clinical Dementia Rating Scale – Sum of Boxes score at through Day 104.

9.2 Sample Size Determination

In Part 1, patients will be recruited sequentially in separate increasing dose groups, with each group randomizing 6 patients to a specific dose of TB006 and 2 randomized to placebo. If all 3 planned dose levels are investigated, the study will recruit approximately 24 patients in total (18 receiving TB006 treatment at the different dose levels, and 6 receiving placebo).

In Part 2, patients will be randomized to TB006 or placebo in a 1:1 ratio so that approximately 58 patients will be randomized to each group. Randomization in Part 2 will be stratified according to baseline patient severity, with mild AD patients (MMSE 21-24) and moderate-severe AD patients (MMSE \leq 20) in each strata. Patients enrolled at the same TB006 dose level in Part 1, as well as all placebo patients, will be included in the efficacy analyses in Part 2. Thus, the number of patients in each group for the primary efficacy analysis will be approximately 64.

Assuming that the standard deviation of change from baseline Clinical Dementia Rating Scale – Sum of Boxes at Day 104 is 0.5, a total of 128 patients will provide 80% power to detect a mean change from baseline difference of 0.25 at Day 104 using a 2-sided, 2 sample t-test at the 5% level of significance.

9.3 Populations for Analyses

For the purposes of analysis, the following analysis sets are defined:

Full analysis set (FAS)	All patients who are randomly assigned to study drug
Safety analysis set (SAS)	All patients randomly assigned to study drug and who take at least 1 dose of study drug. Patients will be analyzed according to the study drug they actually received
PK analysis set (PKS)	All patients who received at least 1 dose of TB006 and have at least 1 post-dose blood sample with measurable TB006 concentrations
PD analysis set (PDS)	All patients who received blinded study drug and have at least 1 post-dose evaluable PD assessment

The FAS will be used for the analysis of disposition and protocol deviations. The SAS will be used for all other analyses, except specifically for PK and PD. The FAS and the SAS will be the

Protocol TB006AD2102

Protocol Date and Version: 15 Oct 2021; v 3.0

same if all randomized patients are dosed with study drug. The PKS will be used for all PK analyses and the PDS will be used for all PD and efficacy analyses.

9.4 Statistical Analyses

The SAP will be finalized prior to database lock and it will include a more technical and detailed description of the statistical analyses described in this section. This section is a summary of the planned statistical analyses of the most important endpoints including primary, secondary, and exploratory endpoints.

9.4.1 General Considerations

Descriptive statistics will be used to summarize the results of the study. Continuous variables will be summarized by reporting the number of observations, mean, standard deviation, median, minimum, and maximum. For the PK parameters and plasma concentrations, geometric mean and coefficient of variation will also be presented. Categorical/discrete variables will be summarized using frequency tables showing the number and percentage of patients within a particular category. All summaries will be presented by dose group and treatment group.

Baseline values will be taken as the most recent assessment prior to dosing, reported during screening and up to and including Day 1.

9.4.2 Part 1 Primary Endpoints

9.4.2.1 Safety and Tolerability

All AEs will be coded using the most recent version of MedDRA. The incidence of AEs will be summarized by SOC and PT. Similar summaries will be produced for AEs by severity, SAEs, treatment related AEs, and AEs leading to discontinuation. AEs are collected from the first dose of study drug, thus all AEs are considered treatment emergent AEs.

The ECG results will be presented by visit, summarizing the continuous measurements based on the average of triplicate values, including the QT, QTc, QRS, RR, PR intervals, as well as change from baseline values, and clinically significant changes in heart rate and rhythm.

Reported values and change from baseline values of hematology, clinical chemistry and urinalysis (and the determinations relevant to the normal ranges and appropriate clinically significant or CTCAE toxicity gradings) will be summarized by laboratory test for each assessment day, using appropriate descriptive statistics.

Vital signs (systolic and diastolic blood pressure, pulse rate, respiratory rate, and oral temperature) will be summarized by assessment day showing absolute values, change from baseline values, and clinically significant changes (including orthostasis) using appropriate descriptive statistics.

Physical and neurological examinations will be summarized by assessment day showing shift from baseline.

Protocol TB006AD2102

Protocol Date and Version: 15 Oct 2021; v 3.0

The C-SSRS assessments will be presented in a by-subject listing.

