10.3 Appendix 3: Liver Safety: Suggested Actions and Follow-up Assessments

Phase 1 liver chemistry stopping criteria define liver injury, evaluate liver event etiology, and are considered in dose escalation decisions.

Table 9. Phase 1 Liver Chemistry Stopping Criteria and Follow-up Assessments

Liver Chemistry Stopping Criteria			
ALT-absolute	Alanine aminotransferase (ALT) \geq 3 × upper limit of normal (ULN) If ALT \geq 3 × ULN AND bilirubin \geq 2 × ULN (> 35% direct bilirubin) or international normalized ratio (INR) > 1.5, report as a serious adverse event (SAE) ^{a,b}		
	See additional actions and follow-up assessments below		
	Required Actions and Follow-up Assessments		
Actions		Follow-Up Assessments	
 Report the ev 24 hours Complete the (CRF), and co collection too criteria for an Perform liver assessments Monitor the pabnormalities 	discontinue study drug ent to the sponsor within liver event case report form complete an SAE data il if the event also met the SAE ^b function follow-up catient until liver function test resolve, stabilize, or return ee MONITORING)	 Viral hepatitis serology^c Obtain INR and recheck with each liver chemistry assessment until the transaminases values show downward trend Serum creatine phosphokinase (CPK) and lactate dehydrogenase (LDH) Fractionate bilirubin, if total bilirubin ≥ 2 × ULN Complete blood count with differential to assess eosinophilia Record the appearance or worsening of 	
 MONITORING: If ALT ≥ 3 × ULN AND bilirubin ≥ 2 × ULN or INR > 1.5 Repeat liver function tests (include ALT, aspartate transaminase [AST], alkaline phosphatase, bilirubin and INR) and perform liver function follow-up assessments within 24 hours. Monitor patient twice weekly until liver function test abnormalities resolve, stabilize, or return to baseline. 		 Record the appearance of worsening of clinical symptoms of liver injury, or hypersensitivity, on the AE CRF Record use of concomitant medications (including acetaminophen, herbal remedies, and other over-the-counter medications) on the concomitant medications CRF Record alcohol use on the liver event alcohol intake CRF If ALT ≥ 3 × ULN AND bilirubin ≥ 2 × ULN or INR > 1.5: 	

Protocol TB006AD2102

Protocol Date and Version: 15 Oct 2021; v 3.0

 A specialist or hepatology consultation is recommended.

If ALT \geq 3 × ULN AND bilirubin < 2 × ULN and INR \leq 1.5:

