12.2. LABORATORY RESULTS

In the context of this study the difference between potentially clinically important (PCI) and PCS results are defined as follows:

- A PCS result is defined as an abnormal laboratory assay result marked as clinically significant in the Investigator's opinion.
- A PCI result is defined as a laboratory assay result that meets criteria tested against as used by the local laboratory for identifying as PCI.

[figure not shown]
The following subject safety laboratory result items are planned to be listed using the SAS for both protocol parts:

- Chemistry
- Hematology
- Urinalysis
- Drug and Alcohol Screening
- Abnormal results
- PCS results
- PCI results

The following local laboratory result items are planned for table presentation, by treatment groups for each applicable visit using the SAS:

- Chemistry:
 - CFB with descriptive statistics
 - Shift from Baseline with summary statistics
- Hematology:
 - CFB with descriptive statistics
 - Shift from Baseline with summary statistics
- Urinalysis:
 - CFB with descriptive statistics for numeric results
 - Qualitative summary of Urinalysis
- PCI laboratory results as tested against local laboratory criteria set (see Appendix IV: Potentially Clinically Important Values for list of criteria)
- Marked abnormalities, including the following criteria:
 - Alanine aminotransferase (ALT) $> 1.5 \times$ upper limit of normal (ULN)
 - Bilirubin $> 1.5 \times$ ULN (where if fractioned, direct bilirubin $\geq 35\%$)
 - ALT or aspartate aminotransferase (AST) $> 3 \times$ ULN and total bilirubin (TBL) $> 2 \times$ ULN and alkaline phosphatase (ALP) $> 1.5 \times$ ULN (Hy's law)

A list of local laboratory assays planned to be performed can be found in Appendix III: Appendix III: Summary of Laboratory Assays Performed. The planned timings of laboratory sample collection are given in Appendix I: Schedule of Assessments and Procedures.

The following ECG listings will be presented for both protocol parts using the SAS:

- Quantitative results containing all the measurements listed in Table 3.
- Potentially clinically significant results.

The following ECG summary tables are planned, by treatment groups using the SAS:

- CFB with descriptive statistics on all the measurements listed in Table 3.
- Categorical Outliers and marked abnormalities, including the following criteria:

For marked abnormalities:

- QTcB > 450 (msec) for male subjects.
- QTcB > 470 (msec) for female subjects.

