Appendix IV: POTENTIALLY CLINICALLY IMPORTANT VALUES

The following table contains a list of ranges used by the laboratory to flag critical laboratory values which will also be used in this study to identify any potentially clinically important values within the table and listings presentations. If a planned laboratory assay does not have applicable PCI criteria limits, that assay is not included in the below table.

Laboratory Category	Assay	Unit	PCI Criteria Value Limits	
			Lower	Upper
Chemistry	Albumin	g/dL	2.0	6.0
	Alkaline Phosphatase	IU/L	NA	200
	Alanine Aminotransferase	IU/L	NA	150
	Aspartate Aminotransferase	IU/L	NA	150
	Bilirubin	mg/dL	NA	2.50
	Blood Urea Nitrogen	mg/dL	NA	30.0
	Calcium	mg/dL	7.0	13.5
	Glucose	mg/dL	40	250
	Potassium	mmol/L	3.2	6.0
Hematology	Sodium	mmol/L	130	150
	Hematocrit (Female)	%	24.0	54.0
	Hematocrit (Male)	%	24.0	60.0
	Hemoglobin (Female)	g/dL	8.0	18.0
	Hemoglobin (Male)	g/dL	8.0	20.0
	Lymphocytes	0^3/uL	0.50	NA
	Neutrophils	0^3/uL	1.00	NA
	Platelets	0^3/uL	75	750
Other Screening Tests	Leukocytes	0^3/uL	2.5	25.0
	Human immunodeficiency virus (HIV)		Positive	
	COVID19		Positive	
	Opiates		Positive	
	Methadone		Positive	
	Buprenorphine		Positive	
	Methamphetamine		Positive	
	Cocaine		Positive	
	Amphetamines		Positive	

Certificate Of Completion

Envelope Id: 503598ABA6D14CA8B5F54D0BDEF7031E
Subject: Please DocuSign: TB006AD2102_SAP_Ver 2.0_11Apr2022.docx
Source Envelope:
Document Pages: 50
Certificate Pages: 5
AutoNav: Enabled
EnvelopeD Stamping: Disabled
Time Zone: (UTC-05:00) Eastern Time (US & Canada)

Status: Completed

Envelope Originator:
[REDACTED]**Record Tracking**

Status: Original
4/12/2022 3:31:21 AM

Holder: [REDACTED]
[REDACTED]

Location: DocuSign

Signer Events**Signature****Timestamp**

Security Level: Email, Account Authentication
(Required)

Signature Adoption: Pre-selected Style

Signed by link sent to [REDACTED]

Signature ID:

053E504E-ECB2-49B9-B7E7-31AE1A775A71

Using [REDACTED]

Sent: 4/12/2022 3:32:45 AM

Viewed: 4/12/2022 3:33:05 AM

Signed: 4/12/2022 3:33:41 AM

With Signing Authentication via DocuSign password

With Signing Reasons (on each tab):

I am the author of this document

Electronic Record and Signature Disclosure:
Not Offered via DocuSign

[REDACTED]
[REDACTED]

Security Level: Email, Account Authentication
(Required)

Signature Adoption: Pre-selected Style
Signed by link sent to [REDACTED]
Signature ID:
A3EA3B5A-E669-4A04-A339-3E173E8742DB
Using [REDACTED]

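### SAP 12.2 has no by-arm outlier count for creatinine, CPK or eosinophils and no row at the protocol's ALT ≥ 3 × ULN criterion, the ECG summaries omit rhythm, and SAP section 8 declares none of this

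*Protocol*

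**What the plan says.** **Protocol, laboratory.** Section 9.4.2.1 (Part 1 primary safety) says that reported values and changes from baseline, with their position against the normal range and appropriate "clinically significant or CTCAE toxicity gradings) will be summarized by laboratory test for each assessment day".

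**Protocol, ECG.** The same section promises a summary of "clinically significant changes in heart rate and rhythm".

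**Protocol, liver.** Appendix 3 says: "Phase 1 liver chemistry stopping criteria define liver injury, evaluate liver event etiology, and are considered in dose escalation decisions". Table 9 sets the single-analyte criterion at ALT ≥ 3 × ULN. It treats ALT ≥ 3 × ULN with either bilirubin ≥ 2 × ULN (> 35% direct) or INR > 1.5 as possible severe liver injury, reportable as an SAE.

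**SAP, laboratory tables.** Section 12.2 opens its table list with "The following local laboratory result items are planned for table presentation, by treatment groups for each applicable visit using the SAS". The list then gives:
- change and shift from baseline for chemistry and haematology;
- "PCI laboratory results as tested against local laboratory criteria set", with the limits in Appendix IV;
- three marked-abnormality rows: ALT > 1.5 × ULN; bilirubin > 1.5 × ULN with a direct-fraction condition; and ALT or AST > 3 × ULN with bilirubin > 2 × ULN and ALP > 1.5 × ULN.

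Results marked clinically significant by the investigator (PCS) are in the listings but not among the tables. CTCAE grade is tabulated in section 12.1, for adverse events only.

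**SAP, Appendix IV.** The coverage rule is: "If a planned laboratory assay does not have applicable PCI criteria limits, that assay is not included in the below table". The ALT entry is "Alanine Aminotransferase IU/L NA 150".

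**SAP, ECG.** Table 3 holds QT, QTcB, QRS, PR and heart rate. Potentially clinically significant ECG results are listed.

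**SAP section 8.** The only difference from the protocol that it names is the dose-proportionality assessment.

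**The concern.** Safety is a primary objective of Part 1 and a secondary objective of Part 2. A laboratory signal often appears as a few patients with large excursions rather than as a shift in the mean, which is why a count by grade or threshold is promised alongside descriptive statistics.

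In the SAP, that count depends on whether the laboratory happens to hold a critical-value limit for the assay. For creatinine, CPK and eosinophils it does not. For ALT, where the protocol has defined its own threshold and uses it in dose-escalation decisions, the SAP counts patients at other cut-offs. A reader of the report could not take from the planned tables how many patients per arm reached the protocol's liver criterion, how many had a marked creatinine or CPK rise, or how many developed a new rhythm abnormality.

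**Working it through.** The plan states no numerical figure on this point to reproduce. The check is a coverage comparison and one unit conversion.

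**1. Coverage of Appendix IV.**
- Protocol Table 5 blood assays: 20 chemistry + 13 haematology = 33, counting total and direct bilirubin separately.
- Appendix IV limits: 10 chemistry (albumin, ALP, ALT, AST, bilirubin, BUN, calcium, glucose, potassium, sodium) + 6 haematology (haematocrit, haemoglobin, lymphocytes, neutrophils, platelets, leukocytes) = 16.
- Without a limit: 33 − 16 = 17. Creatinine, CPK and eosinophils are among them, and none of the three is in the marked-abnormality rows.

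**2. What remains for those three assays.**
- Change from baseline by arm and visit. Under SAP 9.1 this includes the maximum, so one extreme value per arm and visit is visible, but not the number of patients with a marked value.
- Shift from baseline. The SAP does not define the categories. If they are low/normal/high, they show direction, not degree.
- Adverse events by CTCAE grade, for findings the investigator reports. Protocol 10.2.1 includes clinically significant laboratory results in the AE definition; protocol 8.2.4 asks the investigator only to consider recording relevant changes as AEs.

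**3. ALT against Table 9.** The documents give no ULN, so I assume 30 to 60 IU/L. Multiple of ULN at the Appendix IV limit = 150 / ULN; criterion in IU/L = 3 × ULN.

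| Assumed ULN (IU/L) | 3 × ULN (IU/L) | 150 / ULN |
|---|---|---|
| 30 | 90 | 5.00 |
| 35 | 105 | 4.29 |
| 40 | 120 | 3.75 |
| 45 | 135 | 3.33 |
| 50 | 150 | 3.00 |
| 55 | 165 | 2.73 |
| 60 | 180 | 2.50 |

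Below a ULN of 50, a patient can meet the criterion without reaching the 150 IU/L limit (at ULN 40, any value from 120 up to 150). Above 50, a patient can pass 150 IU/L without meeting the criterion. The other row, > 1.5 × ULN, uses the same ALT limit as protocol exclusion criterion 8 and mixes patients at the criterion with much milder rises (at ULN 40, it starts above 60 IU/L).

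**4. Combined liver row.** The SAP row requires ALP > 1.5 × ULN as well. Table 9 and its footnote on severe liver injury contain no ALP condition, and they accept INR > 1.5 as an alternative to bilirubin, which the SAP row does not use. A patient meeting the protocol definition with ALP at or below 1.5 × ULN is not counted. The two must be reconciled.

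**5. Discontinuation as a proxy.** SAP 12.1 defines an AE leading to discontinuation by withdrawal from the study. Protocol Appendix 3 lets a patient who stops drug on the liver criterion stay in follow-up, so that table need not capture these patients.

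**6. ECG.** Heart rate is covered by an outlier row (increase ≥ 30% with a rate > 90 bpm). Rhythm has no table. Protocol 8.2.3 records a clinical interpretation in Part 1 and the investigator's interpretation in Part 2, so the data exist.

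**The case against.** The strongest reply is that the safety tables are fuller than this suggests, and much of it stands.

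- **Listings only?** A reader might infer that a difference in creatinine, CPK or ALT would appear only in listings. The documents do not support that: change (with maxima) and shift are tabulated by arm for all chemistry and haematology.
- **AE route.** Clinically significant laboratory and ECG findings fall within the AE definition in protocol 10.2.1, and protocol 7.2 says new clinically relevant ECG findings should be reported as AEs. Those reported reach the by-arm tables by CTCAE grade. This stands, but it depends on the investigator's judgement and reporting and does not apply a uniform threshold.
- **Weak promise.** The protocol's wording is an alternative, qualified as appropriate, in a section that calls itself a summary. It does not require a CTCAE grade for every analyte, and the Appendix IV table can be read as meeting it for the 16 assays covered. That stands, but it does not help assays that receive neither form of summary.
- **17 of 33.** This overstates the problem if taken as its size. The list includes lipids, TSH, HbA1c, red-cell indices and others for which no consequence is argued. Direct bilirubin, also on it, does enter one liver row as a qualifier.
- **ALT.** It has two by-arm cut-offs, and at a ULN of 50 one coincides with the criterion. The ALT point is a mismatch of thresholds, not an absence of severity information.
- **Mock shells.** Shift categories may be defined there. They were not available, so I treat the categories as undefined rather than inadequate.

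**Conclusion.** The point holds in limited form. Three analytes (creatinine, CPK, eosinophils) have no by-arm count of marked values. No row counts ALT ≥ 3 × ULN, and the nearest fixed limit lies anywhere from 5.0 to 2.5 × ULN over the assumed ULN range of 30 to 60 IU/L. The combined liver row carries an ALP condition that the protocol's severe liver injury definition lacks. The promised rhythm summary has no table. SAP section 8 declares none of this.

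The stronger conclusion, that the arms could not be compared on laboratory severity at all, is not supported, because of the change, shift and AE tables. In Part 1, with 24 patients, the listings can be read patient by patient; the loss is greater in Part 2, with 116.

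Two assumptions matter. The ULN is not in the documents. Also, protocol 9.4.5 refers Part 2 safety presentation to its own section number; I take it that the Part 1 description in 9.4.2.1 is meant.

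This is more than missing detail: the SAP drops a summary that the protocol promises for a primary objective of Part 1.

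**What to change.** In SAP 12.2 add, by treatment group:
- an ALT ≥ 3 × ULN row that matches protocol Table 9;
- worst post-baseline CTCAE v5.0 grade, or an equivalent outlier row, for creatinine and CPK;
- an outlier row for eosinophils.

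Reconcile the combined liver row with the definition in protocol Appendix 3, or state why they differ. Define the shift categories. In the ECG section add a by-arm shift table of the recorded interpretation and rhythm. If any of these is not done, declare the departure in SAP section 8.

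The cost is SAP wording and a few extra tables from data already collected, with no new assessments. The thresholds should be fixed before unblinding, since rows added afterwards would be post hoc.
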